**Efficacy of Low-Frequency, High-Intensity Ultrasound  
for Reduction in Subdermal Adipose Layers**

Device Investigated: Ultimate Contour Body Sculpting Device

Indication Studied: Application of ultrasound for non-invasive waist circumference reduction.

A randomized, blinded comparison of waist circumference reduction of an active test group vs. a placebo control in adults.

Sponsor: CAO Group, Inc.

Protocol ID: 005-00036-8

Development Phase: Performance Validation

NCT ID: Not Yet Assigned

Anticipated Initiation Date: 15 December 2019

Anticipated Completion Date: 1 May 2020

Document Date: 10 October 2019

## **SYNOPSIS**

Sponsor: CAO Group, Inc.

Device Investigated: Ultimate Contour Body Sculpting Device

Study Title: Efficacy of Low-Frequency, High-Intensity Ultrasound for Reduction in Subdermal Adipose Layers

Anticipated Initiation Date: 15 December 2019

Anticipated Completion Date: 1 May 2020

### **Objectives**

The purpose of this study is to evaluate principally the effectiveness, and secondarily the safety, of external application of lower frequency ultrasound to the waist/abdominal region of adults to achieve a reduction of adipose cells/tissues in the subcutaneous region. The application of higher frequency (200kHz to 3MHz) ultrasound for this purpose has previously been demonstrated and such devices have received clearance for treatment in the United States. The question remains whether application of ultrasound at a lower frequency (35kHz to 45kHz) can achieve comparable results without introducing any new or elevated risks to the patient. This study seeks to answer this question.

### **Methodology**

Samples of the test device (Ultimate Contour Mini by CAO Group, West Jordan, Utah, U.S.A.) will be provided for the test. The devices consist of a touch screen interface whereby the operator may select the intensity of the delivered energy and the duration of treatment. The device features a single output cable to which is attached the ultrasound handpiece assembly. For the purposes of this test, the duration of treatment will be set at 30 minutes, and the intensity set at Level 4 (the maximum the device is capable of).

Application of the ultrasound energy consists of applying a treatment gel or liquid to the patient's skin (to eliminate air gaps between the applicator and the skin) and gently kneading the skin in circular motions, slowly progressing across the surface of the treatment area, making methodical passes until the entire treatment area has been exposed, then returning to the origin point and repeating this application approach.

Following treatment, the patient will be asked regarding the extent of discomfort experienced during the ultrasound application, and assessment will be made by a blinded, independent evaluator whether a number of visible skin conditions are observed or experienced by the patient.

Prior to the first treatment, the patient's weight and height will be measured by the blinded, independent evaluator, and the patient's waist circumference measured using a constant-tension flexible tape measure. Each patient will be treated a total of three (3) times, with a gap of 6-8 days between each treatment. Prior to each treatment, the patient will be weighed. Following the final treatment, the patient will be advised of support mechanisms (healthy diet, exercise, and so forth) to support a successful outcome. At 1, 4, and 12 weeks after the last treatment, the patient will be recalled for a final measurement and review of any outstanding adverse events. Study success shall be determined by achieving at least 1 inch of waist reduction between the initial measurement and the 12-week follow-up.

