#### **INVESTIGATORS AND ENVIRONMENT OF TREATMENT**

All testing conducted under this investigation will be performed at a single site, an existing dermatology practice located in Midvale, Utah. This setting is representative of the medical office environment under which the device would be used in the market. Consistent with this setting, patients will be scheduled for treatment and upon arrival have the procedure performed, along with appropriate pre-treatment and post-treatment assessment and instructions, and then allowed to depart. The principal investigator for this study has no contractual or financial relationship with the sponsor or with the specification developer. Additional research staff, in the persons of medical staff and assistants already present at the study site, shall assist with the performance of this study. Treatment and measurement activities shall be conducted in separate rooms, and shall be performed by different staff. Assessment shall be performed by licensed physicians.

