The device in question, presently branded as the Ultimate Contour Mini, is at the stage of development where functional demonstration devices have been constructed and assembled. The design at present is representative of the final released configuration to the extent that third-party safety testing and certification has been conducted on the device and the device demonstrated to be safe relative to the design and constructional requirements of IEC 60601-1 (3rd Edition) for safety of electrical and electronic medical devices and systems, as well as IEC 60601-1-2 (3rd Edition) for electromagnetic compliance safety and performance of electrical and electronic medical devices and systems.

The study has a fixed endpoint of three (3) treatment sessions and three follow-up visits per patient, to the extent that a sufficient quantity of patients have completed the study. Given that a gap of 6-8 days will exist between treatments, the scheduling of patients will be staggered as necessary to best utilize investigator and equipment resources, with the overall course of the study treatments is not expected to exceed 6 weeks of total study time. The follow-up visits are mandated to occur at intervals of one, four, and twelve (12) weeks from the date of final treatment. Once all patient treatments are completed, analysis of the data shall be performed by the sponsor (and reviewed by an independent statistical resource) to determine the extent of success in achieving the primary and secondary objectives.

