## **STUDY OBJECTIVES**

**PRIMARY** - The primary objective of this study is to determine if the application of lower frequency (35kHz to 45kHz) ultrasound energy to the waist/abdominal region of the human body is capable of effecting a reduction in the amount of subcutaneous adipose cells and/or tissue to an amount of at least 1 inch and to a statistically significant level. Determination of the reduction in this adipose tissue is achieved via measurement of the body circumference that includes the abdominal area that was treated, and comparing measurements prior to the initial treatment with measurements after the entire treatment regime is concluded. Per the proposed clinical mechanism of action, the disrupted tissue is cleared by the lymphatic system which facilitates excretion or elimination of the disrupted tissue contents. Having been eliminated, the patient should exhibit a reduction in waist circumference. For this objective to be successfully achieved, a reduction in waist circumference of at least one inch must be demonstrated at a point of 12 weeks after the last of three treatment sessions has been applied.

**SECONDARY** - The secondary objective of this study is to assess the safety of this device. Assessment is made by having the patient rate the treatment experience and report any symptoms, side effects, or associated abnormal conditions. Additional assessment is made by the investigators to qualitatively confirm if visually detectable abnormal conditions (example: edema) are presented following the treatment. Success is determined by whether the patients indicate that any discomfort experienced during the treatment, and following the treatment that are directly attributable to the treatment, along with an absence of side-effects or abnormal conditions directly attributable to the treatment, create a risk/benefit condition where the benefit of treatment is regarded to outweigh the risks and temporary discomfort. Quantitatively, the benefit is regarded to outweigh the risk when: 1) No patients report a pain rating of 4 or higher on the Stanford Pain Scale, 2) No patients exhibit any side effects or abnormal conditions at the conclusion of the final treatment, and 3) No patient who was included in the Test group reports that the treatment regimen was unsuccessful.

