After attachment of the handpiece, the operator selects which treatment type (US or RF) is to be done. The device then presents only two parameters for operator to adjust: the duration of the treatment, and the relative intensity of the applied energy. The duration can be selected from 10, 20, 30, or 40 minutes duration. The intensity is selected from a comparative rating Level of "1, 2, 3, or 4", with Level 4 being the maximum energy level the device can output and Levels 1 through 3 being at staggered levels less than the maximum. Once the settings are selected, the operator places the device into a Ready state. At this point, the handpiece is placed in contact with the skin and the operator presses a button on the screen to Activate the handpiece. The unit applies energy to the handpiece at the selected intensity Level and the unit begins to count down from the selected time duration. Generally, the operator allows the device to operate until the selected time elapses, at which point the device automatically returns to the Ready state and beeps to inform the operator the cycle is complete. The operator may also stop the treatment at any time, either by pressing the stop button on the screen or activating a separate emergency stop button located on the device. During treatment, the device monitors the temperature of the handpiece (and by contact, the temperature of the skin) via temperature sensors located in the handpiece and in direct contact with external metal surfaces of the handpiece that contact the skin. If excessive temperature is measured, the device halts operation of the handpiece. For the purposes of this study, the device will be set at a treatment time of 30 minutes and an intensity level of 4.

Adjunctive activities associated with the treatment will also be performed. These included conversation with the patient about what to expect during the individual treatments and overall outcomes of the entire regimen, as well as instructions to the patient at the conclusion of the study regarding care and proper lifestyle habits. All of these adjunctive activities are described in the operator's manual for the device, and the clinicians will be instructed on the presence of these consultative activities in the manual and the execution of these activities for the purposes of this study.

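### Diet and exercise advice given before the week-12 waist measurement enters the 1-inch success criterion, and the synopsis and protocol body conflict on when it is given

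*Combined protocol and SAP*

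**What the plan says.** The Synopsis, under Methodology, gives this order. After the third treatment: "Following the final treatment, the patient will be advised of support mechanisms (healthy diet, exercise, and so forth) to support a successful outcome". Recalls at 1, 4 and 12 weeks come next, and then the decision rule: "Study success shall be determined by achieving at least 1 inch of waist reduction between the initial measurement and the 12-week follow-up".

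Study Objectives (Primary) asks whether the ultrasound energy "is capable of effecting a reduction in the amount of subcutaneous adipose cells and/or tissue to an amount of at least 1 inch", to be shown 12 weeks after the last treatment. It does not mention advice.

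Device description and settings says "Adjunctive activities associated with the treatment will also be performed", and counts among them "instructions to the patient at the conclusion of the study regarding care and proper lifestyle habits". It refers to the operator's manual for the details; the manual is not among the documents.

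Study configuration describes a single arm in which every eligible candidate is treated. The title page, the Statistical Methods part of the Synopsis, and Sequence and duration of study period refer instead to a control or to study groups.

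The primary analysis (Statistical methods planned) is a single-factor ANOVA on change in waist circumference, with no covariate. The Synopsis schedules weighing before treatments. The Follow-up steps list waist, surveys, a diary of unusual sensations and events, and adverse-event review, with no weight and no diet or exercise record.

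**The concern.** Waist circumference is what diet and exercise advice acts on, and the synopsis gives the advice in order to help the outcome. If it is given at the end of treatment, a second intervention aimed at the endpoint runs through the whole follow-up period before success is decided. Any effect it has pushes the 1-inch criterion towards success. In a single arm there is no comparison to remove that effect, so the significance test on the change carries it too. A positive result could then be credited to ultrasound when part of it came from the advice, and the data listed for collection would not allow the two to be told apart afterwards. Introduction itself names healthy-lifestyle instruction as something earlier studies did not account for, so the sponsor already regards it as relevant.

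**Working it through.** **1. When is the advice given?**
- Synopsis, Methodology: after the final treatment, before the recalls are described.
- Device description and settings: "instructions to the patient at the conclusion of the study regarding care and proper lifestyle habits".
- Introduction counts follow-up as part of the study: "The study has a fixed endpoint of three (3) treatment sessions and three follow-up visits per patient".
- Monitoring (Audit of the Records) uses the same end-of-study phrase for the full audit, which must confirm that adverse effects were followed to conclusion. There it can only mean after follow-up.
- The listed visit steps contain no advice step at either point. This is weak evidence, because they also omit the weighing that the Synopsis requires.

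The most natural reading is that the synopsis puts the advice before the endpoint and the body puts it after.

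**2. What does the advice enter, if the synopsis is followed?** Assume additive effects: device u and advice a, in inches.
- Single arm: change from baseline = u + a. Both the 1-inch criterion and the test of the change contain a.
- Control arm given the same advice: between-arm difference = (u + a) − a = u, so the comparison is clean. The active arm's change from baseline is still u + a, so the 1-inch criterion still contains a.

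**3. How long could the advice act?** Two gaps of 6–8 days give 12–16 days from treatment 1 to treatment 3; 12 weeks is 84 days; total 96–100 days. Share after treatment 3: 84/100 = 84.0% to 84/96 = 87.5%. These are nominal: the 6–8 day gap is only preferred in Sequence and duration of study period, and the advice is assumed to be given on the day of treatment 3. This is calendar exposure, not bias.

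**4. How much could it matter?** The plan's own sample size comes first, because it supplies the SD: 2 × (1.96 + 0.84)² × 1.5² / 1.0² = 35.28, rounded up to 36. The t-test version gives 36.3, rounded up to the stated 37. The figure reproduces and is not at issue.

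The documents give no value for a, so the values below are assumptions. I also assume that 1.5 inches is the SD of the change, that success means a mean reduction of at least 1 inch, and that the single-arm test compares the mean change with zero. With the target of 40 completers, SE = 1.5/√40 = 0.237 inch.

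Chance that the mean reaches 1 inch = 1 − Φ((1 − u − a)/SE). With u = 0.75, the typical response quoted in Sample size:

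| Assumed a (inch) | (1 − u − a)/SE | Chance |
|---|---|---|
| 0 | 1.05 | 15% |
| 0.25 | 0 | 50% |
| 0.50 | −1.05 | 85% |

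With u = 0 (no device effect):

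| Assumed a (inch) | Mean reaches 1 inch | Change significant, two-sided 0.05 |
|---|---|---|
| 0.25 | 0.1% | 18% |
| 0.50 | 1.8% | 56% |

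**The case against.** **The body may already defer the advice.** If the body's wording governs, there is no confounding. That stands as a reading, but the synopsis says otherwise, and a site could follow either. One might try to reconcile the two through the Introduction's phrase "is not expected to exceed 6 weeks of total study time", as if the study ended with treatment. The subject of that phrase is the course of treatments, so it does not move the end of the study. Nor does the general mention of visits "along with appropriate pre-treatment and post-treatment assessment and instructions", under Investigators and Environment of Treatment, settle the timing.

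**The advice may be deliberate.** Testing a device together with its labelled instructions is legitimate, and the manual might require them. This stands; the objective and conclusion should then say so. A reader might infer that the objective claims an effect of ultrasound alone. That word is not there: the objective names ultrasound and is silent on advice.

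**The attribution problem really comes from the unclear design.** Largely true for the significance test: an equally advised control would remove the advice effect there, and without a control, deferring the advice does not establish causation. It does not dispose of the 1-inch criterion, which is a change from baseline under either design.

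**The surveys might record lifestyle.** Their content is not reproduced, so this cannot be excluded. No planned analysis uses such an item to adjust the primary result.

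**Conclusion.** The point holds in this form: the synopsis and body conflict on when lifestyle advice is given, and if the synopsis is followed, the 1-inch change from baseline includes any effect of the advice with nothing planned to separate it. That is so with or without a control arm. In a single arm it also affects the significance test.

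The size is unknown. Under the stated assumptions, an advice effect of 0.25 inch on top of a 0.75-inch device effect moves the chance of a 1-inch mean from 15% to 50%.

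Two stronger inferences are not supported. The 84.0%–87.5% share of calendar time does not mean that most of any reduction would be due to advice. Nor would modest advice by itself be likely to produce success: with no device effect, 0.25 or 0.50 inch brings the mean to 1 inch in only 0.1% or 1.8% of trials. The advice matters mainly when added to a real device effect that falls short of the threshold. The change is worth making because it is cheap and removes an avoidable co-intervention.

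**What to change.** Change Methodology in the Synopsis to agree with Device description and settings: lifestyle advice goes to every patient only after the week-12 waist measurement. Add it as the last step of the 12-week visit under Follow-up, so that the timing is explicit.

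If the sponsor wants early advice as part of intended use, give it identically to all patients at the final treatment visit, and state the primary objective and the 1-inch conclusion as ultrasound plus lifestyle instruction.

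In either case, report a single-arm result as change from baseline after treatment, not as an effect shown to be caused by ultrasound.

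The cost is a few lines of text, with no added visits, staff or measurements. Deferral may depart from the regimen in the operator's manual, which the sponsor should check; the alternative narrows the claim. Deferral does not make up for the lack of a control in a single arm.

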## **Statistical Methods**

Single factor ANOVA analysis will be used to determine if the extent of circumference reduction in the test group is statistically significant over changes in the control group. Additional correlation assessment will be performed to identify any potential relationships between patient data sets, and single-factor ANOVA assessment applied to those correlations as applicable. Missing or incomplete data shall be populated using least-favorable data from participants who did complete the study.

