### **Statistical methods planned, including handling data exclusion, analysis of sub-groups if any**

Any patient that did not conclude all three treatments shall be excluded from the analysis. If there are fewer than 37 patients remaining after the study concludes and exclusions are applied, than no analysis shall take place and additional study subject enrolled until a minimum of 40 completed participants exist. In the event that a patient concludes at least one treatment session, but afterwards discontinues

participation in the study, the presence of the patient in the study shall be acknowledged for data analysis purposes. Missing data for such acknowledged participants shall be fulfilled by inserting the least favorable result obtained realized from among all test subjects who did complete the study. Statistical analysis shall then proceed on the fully populated study data.

Primary analysis shall consist of applying the Anova single-factor acceptance test evaluating the change in waist circumference based on the data collected by the tape measure. A confidence of  $P=0.05$  shall be applied. The results of this data shall be directly applied to determining if the primary objective of the study has been met.

A correlation analysis shall be applied to all variable data recorded, as well as key calculations from the data, to identify any potential two-way connections or relationships between sets of data. Any correlations scoring a magnitude of 0.85 or greater shall be discussed and if appropriate, Anova single-factor analysis applied to determine if there is statistical significance to the relationship and any statements that might be supported by the data. Of primary interest is any impact the starting BMI might have on the amount of change, and any impact that gender may impart to the outcome.

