### **Sample size**

A total sample size of a minimum of 40 patients was established for this study. This number is based on

$$n = \frac{2 \cdot (Z_\alpha + Z_\beta)^2 \cdot \sigma^2}{d^2}$$

where:

$Z_\alpha = 1.96$ , based on a confidence of  $P=0.05$  (false rejecting of a true null hypothesis),  
 $Z_\beta = 0.84$ , based on a power of 80% (failure to reject a false null hypothesis),  
 $d = 1.0$  inch reduction in waist circumference as a meaningful/successful change in measurement,  
 $\sigma = 1.50$  inches, based on the evidence presented by a published study under similar treatment parameters and conditions reporting a typical response of 0.75 inches through the umbilical region and assuming some of the population may not respond at all.

The resulting calculation gives a population size of 37. Accounting for possible attrition and adding a generous margin of safety, a recruitment size of 50 individuals is arrived at. Review of the data analysis shall be conducted by an independent entity to confirm the handling and calculation of data, and the conclusions drawn from the data regarding statistical significance.

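### If the placebo-controlled design is kept, the 1-inch threshold names no comparator, yet the sample size uses that same inch as a test-minus-control difference

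*Combined protocol and SAP*

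**What the plan says.** **Design.** The title page describes "A randomized, blinded comparison of waist circumference reduction of an active test group vs. a placebo control in adults". Under Statistical Methods, the synopsis has a single-factor ANOVA to "determine if the extent of circumference reduction in the test group is statistically significant over changes in the control group". Study configuration, in contrast, calls the study single-arm.

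**Size of effect.** The synopsis (Methodology) says: "Study success shall be determined by achieving at least 1 inch of waist reduction between the initial measurement and the 12-week follow-up". Under Study Objectives, the primary objective repeats that "a reduction in waist circumference of at least one inch must be demonstrated at a point of 12 weeks after the last of three treatment" session, and gives the basis of the measure as "comparing measurements prior to the initial treatment with measurements after the entire treatment regime is concluded". Neither place names a comparator for the inch.

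**Significance.** The primary objective also asks for the reduction to be shown "to an amount of at least 1 inch and to a statistically significant level". The section on planned statistical methods says of the ANOVA: "The results of this data shall be directly applied to determining if the primary objective of the study has been met".

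**Sample size.** The formula is n = 2(Zα + Zβ)²σ²/d², with Zα = 1.96, Zβ = 0.84 and σ = 1.50 inches. d is 1.0, described as an "inch reduction in waist circumference as a meaningful/successful change in measurement". The stated result is 37, with a minimum total of 40 and recruitment of 50. No expected change in the control group is given.

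**The concern.** One figure, 1.0 inch, stands for two quantities. In the success rule it is how much patients lose from their own starting measurement. In the sample size formula the factor 2 makes it a difference between two group means. The wording of d follows the first meaning and the formula requires the second.

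If both arms lose some waist for reasons unrelated to ultrasound, that loss counts in full toward the success threshold and is subtracted from the difference the ANOVA has to detect. Two consequences follow. The reported inch may be partly a change that controls also showed. And a device whose users lose exactly the planned inch may have much less power against control than the stated 80%.

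A change in controls is plausible on the plan's own terms. The synopsis has patients advised on diet and exercise after the last treatment, which is before the 12-week measurement, and does not limit this to one arm. The Introduction criticises earlier studies for not allowing for lifestyle instructions.

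**Working it through.** **Inputs.** d = 1.0 inch, σ = 1.50 inches, Zα = 1.96, Zβ = 0.84, minimum total 40 (all from Sample size). Assumed here: 1:1 allocation, σ is the SD of change and equal in both arms, no dropout. Zα = 1.96 is taken as two-sided 0.05. The plan gives no control change, so a range is shown.

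**1. The plan's own figure.**
2 × (1.96 + 0.84)² × 1.5² / 1.0² = 2 × 7.84 × 2.25 = 35.28, rounded up to 36. The two-sample t version gives 36.3, rounded up to 37. The stated 37 is therefore reproduced, but as a number per arm; the matching total is 72 to 74. A one-sample calculation with the same inputs gives 18 (normal) or 20 (t), so 37 is not a single-arm number.

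**2. What d implies.**
d = treated loss − control loss. With a treated loss of 1.0 inch, d = 1.0 requires a control loss of 0. Control losses of 0.25 and 0.5 inch leave differences of 0.75 and 0.5.

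**3. Power of the between-arm test when treated patients lose 1.0 inch.**
Standard error of the difference = 1.5 × √(2/n): 0.474 at 20 per arm and 0.349 at 37 per arm. Noncentrality = difference / standard error. Power is from the noncentral t, which for two groups is the same as single-factor ANOVA.

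| Control loss (in) | Difference (in) | Noncentrality, 20 per arm | Power, 40 in total (20 per arm) | Noncentrality, 37 per arm | Power, 37 per arm |
|---|---|---|---|---|---|
| 0 | 1.00 | 2.11 | 54% | 2.87 | 81% |
| 0.25 | 0.75 | 1.58 | 34% | 2.15 | 56% |
| 0.5 | 0.50 | 1.05 | 18% | 1.43 | 29% |

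The gap between 54% and 81% in the first row comes from using a per-arm number as a total. The fall down each column is the issue raised here.

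**4. Can a device adding less than 1 inch pass?**
Take a treated loss of 1.5 and a control loss of 0.75, so the device adds 0.75 inch. Simulated chance of being significant in favour of the device and also meeting the inch:

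| | Inch judged on treated-arm mean | Inch judged on difference |
|---|---|---|
| 20 per arm | about 34% | about 28% |
| 37 per arm | about 56% | about 24% |

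The gap is small at 20 per arm because significance there already needs an observed difference of about 2.024 × 0.474 = 0.96 inch. At 37 per arm it needs about 1.993 × 0.349 = 0.70 inch, so significance does less to protect the size claim.

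**The case against.** **Control is in the rule.** The primary objective has two parts, and the ANOVA supplies the second part against control. A reader might infer that the control arm plays no role in success; the documents do not support that. A reader might also take the 1-inch rule alone and note that the treated mean (20 patients) of an inert device would reach 1 inch 7%, 23% or 50% of the time at shared losses of 0.5, 0.75 or 1.0 inch. Those figures leave out the significance requirement. With it, an inert device passes only about 1% to 3% of the time at 20 per arm. What stands is narrower: significance shows that the difference is not zero, not that it is an inch.

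**Only the difference matters for power.** Losses of 1.5 against 0.5 inch give the same power as 1.0 against 0. It is therefore too strong to say that the 80% assumes no control loss whatever the treated arm does. The implication holds for a treated loss of exactly 1.0 inch, which is how the plan words d.

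**The advice may come too late to matter.** The section on device description and settings places lifestyle instructions at the conclusion of the study, and the listed steps of the final treatment session do not include them. If they come after week 12, they cannot affect the endpoint. The plan conflicts with itself here. Control change is therefore plausible, not established.

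**The study may be single-arm.** Study configuration says so, and the treatment procedure describes no randomization or sham, although other sections refer to study groups. If so, a within-patient inch fits the design and no control change needs assuming. This objection stands in full and makes the point conditional.

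**Conclusion.** The point holds, conditional on the randomized design of the title page and the synopsis. The size threshold names no comparator, and the sample size treats the same inch as a between-arm difference without stating or justifying a control change.

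At the planned minimum of 40, power for a treated loss of 1.0 inch is about 54% with no control loss, 34% at 0.25 inch and 18% at 0.5 inch. The first of these shortfalls belongs to the separate per-arm and total error; correcting that alone would still leave 56% and 29% at the two nonzero control losses. For a device adding 0.75 inch over a 0.75-inch control loss, placing the threshold on the treated arm instead of on the difference raises the chance of success from about 28% to 34% at 20 per arm. The larger gap, 24% to 56%, belongs to 37 per arm, which is not the planned size, and should not be quoted as the effect on this trial.

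These figures rest on SD 1.5 in both arms, 1:1 allocation, two-sided 0.05, no dropout and assumed control losses.

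**What to change.** First reconcile Study configuration with the title page and the synopsis.

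**If the randomized design is kept:**

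1. In Methodology and Study Objectives, judge the 1-inch size on the point estimate of the test-minus-control difference in mean 12-week change. Report it with its 95% CI, alongside the between-arm significance test. Report the treated arm's own change descriptively.
2. In Sample size, define d as that difference, treat the formula's n as per arm, and state the assumed control change. Restate the power of the significance test at the planned total over a range of control changes, such as 0 to 0.5 inch. Note that the point-estimate condition is met only about 50% of the time when the true difference is exactly 1.0 inch, at any sample size, so the power of the significance test is not the chance of overall success.

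**If the single-arm design is kept:** remove the control wording and the two-sample formula, and describe the inch as an uncontrolled change.

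**Cost.** Protocol wording and a restated power figure; no new visits or measurements. The criterion becomes harder to meet if controls lose waist, and the stated power becomes less favourable. If the sponsor wants to keep 80% power for a treated loss of 1.0 inch, more patients are needed: 35.28 / 0.75² = 62.7, so 63 per arm at a control loss of 0.25 inch, and 35.28 / 0.5² = 141.1, so 142 per arm at 0.5 inch.
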